5.0 Number of Subjects

5.1 The proposed single-site study will be conducted at the University of Houston College of Optometry. Up to 30 subjects will be screened for study inclusion, with the goal of completing 24 subjects.

Source data will be collected on paper case report forms and then double entered electronically into a database by trained personnel prior to locking the dataset for analysis.

5.2 In this within-subject crossover design, a paired T-test will be used to compare visual acuity performance, contact lens discomfort, subjective visual quality and LTB4 concentration following toric lens wear to spherical contact lens wear. We will use a two-sided independent T-test to ensure there are no carry over or period effects in our cross-over design, although it is not anticipated. As a secondary outcome, subjects will be asked their preference of contact lenses in a two-alternative forced choice format.

FULL PROTOCOL TITLE: Toric Contact Lens Digital Performance and Comfort Study

One-sample binomial tests will be used to test the hypothesis that the probability of preference to toric lens and spherical lenses are equally likely. Linear mixed model or generalized linear model, as appropriate, will be carried out to examine the associations between eye comfort, visual performance, subjective visual quality and LTB4 concentration during toric and spherical contact lens wear.

We aim to test the hypothesis that $H_0: \Delta=0$ v. $H_1: \Delta \neq 0$ using a two-sided test with significance level $\alpha=0.05$, where Δ is the underlying benefit for treatment contact lenses versus spherical contact lenses in this cross-over design. Our previous work found that toric correction improved visual acuity compared to spherical correction by 6 and 11 letters for high and low contrast logMAR, respectively ($P < 0.001$).¹⁰ To demonstrate an improvement of this amount or more it will require at least 24 and 15 subjects with a $P=0.05$ and 80% power. The dynamic visual acuity test is novel and has not been used previously to allow sample size estimates. A total of 30 subjects will be enrolled to allow for up to 20% dropout/screen-failure/missing data and have 24 subjects complete. We will randomize an equal number of subjects to each group (i.e., group A receives treatment 1 in period 1 and treatment 2 in period 2; group B receives treatment 2 in period 1 and treatment 1 in period 2).

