Title

Toric Contact Lens Digital Performance and
Comfort Study

NCT number

NCT04772560

Document date

20 Dec 2021

Statistical Plan

The outcome measures for the two contact lens designs were first analyzed using the Grizzle model. The data were tested for the presence of a carry-over effect by examining the average of outcomes in the two periods within subjects between the two sequences of randomization, that is, sphere then toric / toric then sphere. Independent paired T-test or Mann-Whitney test, as appropriate, was carried out to ensure there were no carry-over or period effects at the alpha level of 0.10.¹⁹ The differences in outcome measures between lens designs were examined using a linear mixed model, with fixed factors of sequence and contact lens design to obtain unbiased effect sizes. Estimated means, standard errors and medians and interquartile ranges were reported for each lens design. Estimated means, standard errors, and 95% confidence intervals of the differences between lens designs were also reported. In the presence of any carry-over effects, hypothesis tests were conducted on period one only. Significance was defined as P values of 0.05 or less.

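### After a positive carry-over test the SAP restricts only the hypothesis test to period one and does not say whether the estimate and 95% CI go with it

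*SAP*

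**What the plan says.** All the relevant rules are in the single paragraph of the SAP headed Statistical Plan.

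- **Carry-over test.** It works by "examining the average of outcomes in the two periods within subjects between the two sequences of randomization", and is done "to ensure there were no carry-over or period effects at the alpha level of 0.10".
- **Lens effect.** "The differences in outcome measures between lens designs were examined using a linear mixed model, with fixed factors of sequence and contact lens design". This model uses both periods.
- **Reporting.** "Estimated means, standard errors, and 95% confidence intervals of the differences between lens designs were also reported". No condition on the carry-over result is attached.
- **Fallback.** "In the presence of any carry-over effects, hypothesis tests were conducted on period one only".
- **Decision rule.** "Significance was defined as P values of 0.05 or less".

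Protocol section 5.2 plans a paired t-test and a check for carry-over and period effects. It contains no period-one fallback and no rule for the confidence interval.

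**The concern.** Only the fallback sentence depends on the carry-over result, and it speaks of tests alone. Nothing in the SAP moves the estimate, standard error or interval. Followed to the letter, a flagged outcome gets a P value from a between-subject comparison in period one. Its effect size and interval come from the within-subject analysis that the plan has just declined to test on. The two rest on different data and have very different precision, so they can point in opposite directions on significance. Near visual acuity, the primary endpoint in protocol section 9.1, is exposed in the same way as the secondary outcomes.

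A reader of the results table would expect a P value and a 95% CI in one row to describe one analysis, and would have no means of knowing that they do not.

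**Working it through.** **The plan's own figures.** Protocol section 5.2 gives 24 completers inflated for 20% loss: 24 / 0.80 = 30, which reproduces. The 24 itself cannot be reproduced, because no SD of the paired difference is given. The protocol states that "toric correction improved visual acuity compared to spherical correction by 6 and 11 letters for high and low contrast logMAR" and tests "using a two-sided test with significance level" 0.05 at 80% power. Solving the paired t-test power for the SD that makes n = 24 correct at 6 letters gives 10.05 letters, a standardised effect of 6 / 10.05 = 0.597.

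**Assumptions not in the documents.** Normal data, complete pairs, 12 completers per sequence (equal randomisation, 24 / 2), no period effect, and within-subject correlation ρ of 0.5, 0.7 or 0.9. The SD of a single measurement is then 10.05 / √(2(1 − ρ)) = 10.05, 12.97 or 22.47 letters.

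**Analyses compared**, in 40,000 simulated trials per setting:
1. Flag: t-test of subject averages between sequences, P ≤ 0.10.
2. Period-one test: two-sample t-test, 22 df.
3. Two-period interval: mean within-subject lens difference, 23 df. On complete balanced data this matches the mixed model with sequence and lens.

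A disagreement is P ≤ 0.05 with an interval including zero, or P > 0.05 with an interval excluding it.

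**Results with no true carry-over** (the flag fires in about 10% of analyses):

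| Among flagged outcomes | ρ = 0.5 | ρ = 0.7 | ρ = 0.9 |
|---|---|---|---|
| No lens effect: disagree | 35.9% | 41.5% | 46.3% |
| – of which P ≤ 0.05, CI includes 0 | 33.6% | 39.2% | 43.9% |
| 6-letter effect: disagree | 49.6% | 50.6% | 48.0% |
| – of which P > 0.05, CI excludes 0 | 40.6% | 40.6% | 36.9% |

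A second run with 60,000 trials per setting gave 36, 42 and 47% (no effect) and 50, 49 and 48% (6 letters).

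**Unconditional rate.** 0.10 × 0.36 = 3.6% up to 0.10 × 0.50 = 5.0% of outcomes analysed.

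**Why it happens.** Subject averages and within-subject differences are independent in this setting. The flag therefore leaves the two-period interval unchanged: it excludes zero in about 5% (no effect) or 80% (6 letters) of flagged outcomes, as in all outcomes. The period-one mean shares data with the flag statistic. With no lens effect and no carry-over, period-one P ≤ 0.05 occurs in 35.9, 42.2 and 46.7% of flagged outcomes. The two-stage type I error is 0.90 × 0.05 + 0.10 × (0.359, 0.422, 0.467) = 8.1, 8.7 and 9.2%, against 5% for the two-period analysis alone.

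**Precision.** Two-period CI half-width: 2.069 × 10.05 / √24 = 4.2 letters. Period one: 2.074 × SD × √(2/12) = 8.5, 11.0 and 19.0 letters. Period-one power for 6 letters is 31, 20 and 10%.

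**If carry-over were real.** As an illustration only, with 6 letters of effect and 3 letters of differential carry-over the two-period difference averages 6 − 3/2 = 4.5 letters (75% of the truth). Its interval covers the truth about 89-90% of the time, and 42-44% of flagged outcomes disagree. Other assumed values, with ρ from 0.3 to 0.9, give anything from 6-24% (11 letters, carry-over +6) to 75-94% (6 letters, carry-over −6).

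**The case against.** The strongest reply is that the SAP never says the interval stays on two periods. In a one-paragraph plan, restricting hypothesis tests to period one may be shorthand for restricting the whole comparison. That stands: a reader might infer a rule that keeps the interval on the two-period model, but the text supports only silence. The alternative reading has no supporting text either, so the gap remains.

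A reader might also infer that a disagreement would leave the trial without an answer. The documents do not support this. Significance is defined by the P value, and for a flagged outcome the test is the period-one test. What is missing is the source of the effect size and interval, not the decision rule.

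Nor do the figures show that P values and intervals would often clash across the trial. The 35-50% applies to flagged outcomes only. One could assume 12 independent outcomes and get 1 − 0.9^12 = 72% for at least one chance flag. The documents give endpoint families rather than a count, and the measures are taken on the same people, so independence is doubtful. A flag is also not yet a disagreement. That figure is at most an upper illustration.

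Finally, the size is not independent of the known two-stage problem. With no lens effect, over 90% of the disagreement (33.6 of 35.9 points at ρ = 0.5) is a false-positive period-one result beside an interval that correctly includes zero. At 6 letters most of it is low period-one power. This is correct, and it limits what can be claimed. As to real carry-over, protocol section 5.2 does not expect it, and the documents give no value for it.

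**Conclusion.** The point holds as a gap in specification. The SAP ties only the test to period one, leaves the reporting of differences and intervals unconditional, and does not say which data supply the estimate and interval for a flagged outcome. On the literal reading, with no true carry-over, P value and interval disagree in roughly 35-50% of flagged outcomes, or about 4-5% of all outcomes analysed. These figures rest on 24 completers, a standardised effect of 0.597 or zero, and ρ of 0.5 to 0.9. The 0.597 is back-solved from the sample size and ρ is assumed. The mismatch partly expresses the two-stage procedure's own weaknesses and should be settled together with them. It should be corrected, because the remedy is small and the primary endpoint is affected.

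**What to change.** Add to the SAP: *For each outcome, the estimate, 95% CI and P value come from one and the same analysis.* Then choose one of two forms.

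- **Preferred.** Use the two-period analysis for every outcome. Show the period-one difference, its own CI and its own P value together as a sensitivity result. This removes the mismatch and returns the type I error from about 8-9% to 5% when there is no carry-over. It is more than a wording change, since it abolishes the fallback as a decision rule. The two-period estimate would still be biased if carry-over were real, and the sensitivity result is there to show that.
- **If the fallback is kept.** For any flagged outcome, report the period-one estimate and CI with the period-one P value. The mismatch disappears by construction, but the two-stage error stays and the intervals widen (half-width from about 4.2 to 8.5-19.0 letters under the assumptions above).

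The SAP is dated 20 Dec 2021 and written in the past tense. If the analysis is already done, the same rule can be applied to the tables: state for each flagged outcome which data gave the estimate, CI and P value, and declare any change of analysis as made after the fact. The cost is a sentence and a table layout, plus less favourable intervals for flagged outcomes under the second form.

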9.2 This is a minimal risk study so safety endpoints are not required

10.0 Procedures Involved

10.1 The study is a clinical trial and will be registered on ClinicalTrials.gov prior to subject enrollment.

10.2 Patients will be seen for 5 visits over a period of approximately 1 month. Visit 1 will determine subject eligibility for the study. Visits 2 and 4 are contact lens follow-up visits. Visits 3 and 5 are study outcome visits. Tests of visual performance at a near reading distance will be evaluated with an iPad application developed by [name]. These applications are designed for research purposes only and are not commercially available. The applications can measure reading speed and provide information on how a subject interacts with the electronic device (e.g. blink rate, working distance from the device, scrolling and zooming on the page, etc.).

10.3 Subjects will be randomized to start with either toric lenses or spherical correction (FDA approved lenses will be utilized).

Overview of Visit Procedures (Assessments)

FULL PROTOCOL TITLE: Toric Contact Lens Digital Performance and Comfort Study

A masked examiner will perform all outcome measures.

| | Visit 1 Baseline and Fit Lens 1 | Visit 2 day 3±1 | Visit 3 – day 10±2 | | Visit 4 day 13±1 | Visit 5 day 20±2 |
|--|--|-------------------------|-----------------------|---------------|-------------------------|---------------------|
| | | Follow- up Lens 1 | Outcomes Lens 1 | Fit Lens 2 | Follow- up Lens 2 | Outcomes Lens 2 |
| Informed consent | X | | | | | |
| Ocular/medical/contact lens history | X | | | | | |
| Ocular symptoms (CLDEQ-8) ⁸ | X | | X | | | X |
| Auto-refraction and keratometry | X | | | | | |
| Slit lamp exam with NaFl staining | X | | | | | |
| Manifest refraction | X | | | | | |
| Accommodation and phoria | X | | | | | |
| Near logMAR HCHL & LCHL acuity OU | X | | X | | | X |
| NAVQ survey ⁵ | X | | X | | | X |
| Radner reading sentences, dynamic acuity measurement and functional vision test with iPad ⁴ | X | | X | | | X |
| Tear collection | X | | X | | | X |
| Study lens order randomization | X | | | | | |
| Insertion of CL and settling (15 min) | X | | | X | | |
| Clinical CL vision and fit assessment, over-refraction, and power adjustment if indicated | X | X | | X | X | |
| Removal of study lens and slit lamp exam with NaFl staining | | X | X | | X | X |

FULL PROTOCOL TITLE: Toric Contact Lens Digital Performance and Comfort Study

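### The SAP's period-one-only fallback compares about 12 subjects with 12 others and names no baseline covariate, although Visit 1 values are collected; ANCOVA on them would be a cheap, partial remedy

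*SAP*

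**What the plan says.** The SAP examines carry-over by comparing subjects' two-period averages between the sequences. A t-test or Mann-Whitney test "was carried out to ensure there were no carry-over or period effects at the alpha level of 0.10". If carry-over is found, the instruction is: "In the presence of any carry-over effects, hypothesis tests were conducted on period one only". It does not say which model or covariates that test uses. The only model it specifies is a "linear mixed model, with fixed factors of sequence and contact lens design". Neither the SAP nor protocol section 5.2 mentions a baseline term.

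The visit table in protocol section 10 marks "Near logMAR HCHL & LCHL acuity OU" at Visit 1 and at both outcome visits. The same holds for CLDEQ-8, NAVQ, the Radner, dynamic acuity and iPad tests, and tear collection. The table lists all of these above the randomization and lens-insertion rows. Near visual acuity is the primary endpoint (section 9.1).

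**The concern.** The trial is sized as a paired comparison, in which stable differences between people drop out of the lens contrast. Under the fallback they do not. Period one alone compares people who wore toric lenses first with people who wore spherical lenses first, so between-subject variation enters the error in full. That is where a pre-randomization measure of the same outcome is most useful, and the trial has one for nearly every outcome. The forced-choice preference is an exception.

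At stake are the width of the interval, and the false-positive rate, in the weakest branch of the analysis. A false carry-over signal occurs in 10% of cases for each outcome tested. When it occurs, the sequence groups usually differ by chance, and the unadjusted period-one test carries that chance difference into the lens comparison.

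**Working it through.** **Inputs from protocol section 5.** Two-sided alpha is 0.05. The expected benefit is "by 6 and 11 letters for high and low contrast logMAR, respectively", and "it will require at least 24 and 15 subjects with a $P=0.05$ and 80% power". Thirty are enrolled for 24 completers, with equal allocation, so 12 per sequence.

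**Inputs not in the documents.** These are the SD of the within-subject difference, the correlation between periods (ρw) and the baseline-outcome correlation (ρb). The first is back-solved; the other two are varied.

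**The plan's own figures.** Enrolment reproduces: 24/(1 − 0.20) = 30. The 24 and 15 can be neither confirmed nor refuted without an SD. A paired t-test with 24 subjects has 80% power at a standardized difference of 0.597, so the implied SD is 6/0.597 = 10.05 letters. For 15 subjects and 11 letters it is 11/0.778 = 14.1 letters. The rest uses 10.05.

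**Planned paired analysis.** SE = 10.05/√24 = 2.05 letters, with 80% power for 6 letters.

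**Period one only, unadjusted.** The single-measure SD is 10.05/√(2(1 − ρw)), and SE = SD × √(2/12), with 22 df.

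**Period one with the Visit 1 value.** The SE is multiplied by √((1 − ρb²)(1 + 1/20)), with 21 df. The factor 1 + 1/20 is the average small-sample price of chance baseline imbalance. The ratio does not depend on the SD:

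- ρb = 0.3: √(0.91 × 1.05) = 0.98, a 2% fall
- ρb = 0.5: √(0.75 × 1.05) = 0.89, an 11% fall
- ρb = 0.7: √(0.51 × 1.05) = 0.73, a 27% fall
- ρb = 0.8: √(0.36 × 1.05) = 0.62, a 38% fall
- Break-even: ρb² = 1 − 1/1.05, so ρb ≈ 0.22. At ρb = 0 the ratio is √1.05 = 1.025.

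At ρb = 0.7 the adjusted analysis is worth 12/(0.51 × 1.05) = 22.4 unadjusted subjects per sequence.

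**In letters, with ρw = ρb = r (ignoring the pre-test):**

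| r | SD | SE, unadjusted v adjusted | 95% half-width | Power for 6 letters |
|---|---|---|---|---|
| 0.5 | 10.05 | 4.10 v 3.64 | 8.51 v 7.57 | 29% v 35% |
| 0.7 | 12.97 | 5.30 v 3.87 | 10.98 v 8.06 | 19% v 32% |
| 0.8 | 15.89 | 6.49 v 3.99 | 13.45 v 8.29 | 14% v 30% |

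The two correlations need not be equal. With ρw = 0.5, power is 29% unadjusted, and 30%, 35%, 48% and 62% at ρb = 0.3, 0.5, 0.7 and 0.8.

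**Behaviour after the pre-test.** This was simulated with 12 v 12, no carry-over and no lens effect. The pre-test fires in about 10% of trials. Among those:

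- At r = 0.5, 0.7 and 0.8, the unadjusted period-one test rejects in about 36%, 41% and 45%. ANCOVA rejects in about 21%, 17% and 12%.
- Root mean squared error falls from 7.5–12.7 to 5.4–5.7 letters.
- With ρb = 0.3 the gain is small: false rejection falls only to roughly 35% (29% when ρw is 0.5, more when it is higher).

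Overall type I error of the two-stage procedure is 8.1%, 8.6% and 8.9% unadjusted at r = 0.5, 0.7 and 0.8. With ANCOVA in the fallback it is 6.7%, 6.0% and 5.8%, and 7.4% at ρw = 0.5 with ρb = 0.3.

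**The case against.** The strongest reply is that the power figures do not describe the branch being criticized. The period-one test is run only after the pre-test fires, and the two statistics are correlated. After a false trigger with a true effect of 6 letters, the unadjusted test rejects in about 50–51% of trials and ANCOVA in 45%, 39% and 34% at r = 0.5, 0.7 and 0.8, so the promised gain in power does not appear. This stands as a limit on how the power figures may be read. It does not show harm: the unadjusted test also rejects in 36–45% of such trials when the lenses do not differ, so its higher rejection rate is not sensitivity. Adjustment lowers both false rejection and error of estimation.

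Second, ρb may be low. The documents do not say what correction is worn for Visit 1 acuity. Subjects must be willing to go without their habitual lenses for at least 24 hours, whereas outcomes follow 6–8 hours of study-lens wear. Entry requires CLDEQ-8 below 12 and acuity of 20/25 or better, which restricts range. This stands, and is why the gain is given as a range that includes a small loss.

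Third, the two-stage rule is the larger fault, and adjustment leaves it in place. This also stands.

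Some stronger readings are tempting but unsupported:

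- A reader might infer that baseline was deliberately left out because it cancels within subject. The documents give no such reason; the SAP is silent on the period-one model.
- A reader might count about nine outcomes and put the chance of at least one false trigger at 1 − 0.9⁹ = 61%. That requires independence, which is implausible for acuity and reading measures in the same people. For a single outcome it is 10%, and section 5.2 does not anticipate carry-over.

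**Conclusion.** The point holds as an unspecified covariate in a contingency analysis, where the data to fill it are already collected. The relative gain in SE depends only on the baseline-outcome correlation and the 12 v 12 split. The figures in letters and power also rest on the back-solved SD of 10 letters and on assumed correlations. Twelve per sequence is the completer count; up to 15 (30/2) could have period-one data, which would improve both analyses.

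It would go too far to say that adjustment restores the lost power or removes bias. Measured from the planned 80%, the fallback loses 51, 61 and 66 points at r = 0.5, 0.7 and 0.8, and adjustment returns 6, 13 and 16 of them. After a false trigger the adjusted 95% interval covers the true difference only about 79–88% of the time at these settings, and overall type I error stays above 5%. ANCOVA improves the branch the SAP chose; it does not make choosing that branch by pre-test valid.

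**What to change.** State in the SAP that any period-one-only comparison is an ANCOVA of the period-one outcome on lens, with the same outcome's Visit 1 value as covariate. The same covariate may be added to the mixed model, where it helps subjects with only one period observed and leaves the lens contrast from complete pairs unchanged. How many such subjects there are is unknown, so no size is claimed for that part.

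Preferably, keep the two-period mixed model, with period and baseline terms, as the main analysis whatever the pre-test shows. That addresses the larger fault.

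The cost is a sentence in the SAP, one degree of freedom and no new data, with up to 2.5% of the SE at risk if the baseline proves uninformative. The SAP is dated 20 December 2021 and written in the past tense. If results are already known, the adjusted period-one estimate should be reported beside the unadjusted one and labelled a sensitivity analysis.
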